12.3.4. Changes to Planned Analyses

Any changes to the planned statistical analyses made prior to breaking the blind will be documented in an amended Statistical Analysis Plan approved prior to breaking the blind. Changes from the planned statistical methods after breaking the blind will be documented in the clinical study report along with a reason for the deviation.

13. Data Management

13.1. Data Collection, Processing, and Review

Subject data will be recorded in a limited access secure electronic data capture (EDC) system.

The clinical database will reside on a production server hosted by EDC System. All changes made to the clinical data will be captured in an electronic audit trail and available for review by the sponsor or its representative. The associated RAVE software and database have been designed to meet regulatory compliance for deployment as part of a validated system compliant with laws and regulations applicable to the conduct of clinical studies pertaining to the use of electronic records and signatures. Database backups are performed regularly.

The Investigator provides his/her electronic signature on the appropriate electronic case report forms (eCRFs) in compliance with local regulations. A written signature on printouts of the eCRFs must also be provided if required by local regulation. Changes to data previously submitted to the sponsor require a new electronic signature by the Investigator acknowledging and approving the changes.

Visual and/or electronic data review will be performed to identify possible data discrepancies. Manual and/or automatic queries will be created in the EDC system and will be issued to the site for appropriate response. Site staff will be responsible for resolving all queries in the database.

13.2. Data Retention

The Investigator or Investigational site will maintain, at the investigative site, all essential study documents and source documentation that support the data collected on the study subjects in compliance with ICH/GCP guidelines. Documents must be retained until at least 2 years have elapsed since the formal discontinuation of the clinical investigation of the product. These documents will be retained for a longer period of time by agreement with BSC or in compliance with other country/regional/local regulations. The Investigator will take measures to ensure that these essential documents are not accidentally damaged or destroyed. If for any reason the Principal Investigator or his/her designee withdraws responsibility for maintaining these essential documents, custody must be transferred to an

individual who will assume responsibility and BSC must receive written notification of this custodial change. Sites are required to inform Boston Scientific in writing where paper or electronic files are maintained in case files are stored off site and are not readily available.

13.3. Core Laboratories

The Electrogram and Device Interrogation Core Laboratory will review interrogation data to determine primary endpoints that occur in APPRAISE ATP. Their decisions are based on independent physician review of the data from device interrogation. Responsibilities, qualifications, membership, and committee procedures are outlined in the EGM Adjudication Charter. Separate instructions regarding the core lab charter will be provided.

14. Amendments

If a protocol revision is necessary which affects the rights, safety or welfare of the subject or scientific integrity of the data, an amendment is required. Appropriate approvals (e.g., IRB/EC/FDA/CA) of the revised protocol must be obtained prior to implementation.

15. Deviations

An Investigator must not make any changes or deviate from this protocol, except to protect the life and physical well-being of a subject in an emergency. An investigator shall notify the sponsor and the reviewing IRB/EC of any deviation from the investigational plan to protect the life or physical well-being of a subject in an emergency, and those deviations which affect the scientific integrity of the clinical investigation. Such notice shall be given as soon as possible, but no later than 5 working days after the emergency occurred, or per prevailing local requirements, if sooner than 5 working days.

All deviations from the investigational plan, with the reason for the deviation and the date of occurrence, must be documented and reported to the sponsor using the deviation CRF in the EDC system. Sites may also be required to report deviations to the IRB/EC, per local guidelines and government regulations.

Deviations will be reviewed and evaluated on an ongoing basis and, as necessary, appropriate corrective and preventive actions (including notification, site re-training, or site discontinuation/termination) will be put into place by the sponsor.

16. Compliance

16.1. Statement of Compliance

This study will be conducted in accordance with post market clinical follow up guidelines and will follow the applicable sections of ISO 14155(Clinical Investigation of Medical Devices for Human Subjects – Good Clinical Practice), the relevant parts of the ICH Guidelines for Good Clinical Practices, ethical principles that have their origins in the Declaration of Helsinki, and pertinent individual country laws and regulations. The study shall not begin until the required approval/favorable opinion from the IRB/EC and/or regulatory authority has been obtained, if appropriate. Any additional requirements imposed by the IRB/EC or regulatory authority shall be followed, if appropriate.

16.2. Investigator Responsibilities

The Principal Investigator of an investigational site is responsible for ensuring that the study is conducted in accordance with the Clinical Study Agreement, the clinical investigation plan/, ISO 14155, ethical principles that have their origins in the Declaration of Helsinki, any conditions of approval imposed by the reviewing IRB/EC, and prevailing local and/or country laws and/or regulations, whichever affords the greater protection to the subject.

The Principal Investigator's responsibilities include, but are not limited to, the following.

- Prior to beginning the study, sign the Clinical Study Agreement and comply with the Investigator responsibilities as described in such Agreement.
- Prior to beginning the study, sign the Protocol Signature page documenting his/her agreement to conduct the study in accordance with the protocol.
- Provide his/her qualifications and experience to assume responsibility for the proper
 conduct of the study and that of key members of the site team through up-to-date
 curriculum vitae or other relevant documentation and disclose potential conflicts of
 interest, including financial, that may interfere with the conduct of the clinical study or
 interpretation of results.
- Make no changes in or deviate from this protocol, except to protect the life and physical well-being of a subject in an emergency; document and explain any deviation from the approved protocol that occurred during the course of the clinical investigation.
- Create and maintain source documents throughout the clinical study and ensure their availability with direct access during monitoring visits or audits; ensure that all clinicalinvestigation-related records are retained per requirements.
- Ensure the accuracy, completeness, legibility, and timeliness of the data reported to the sponsor in the CRFs and in all required reports.
- Record, report, and assess (seriousness and relationship to the device/procedure) every adverse event as applicable per the protocol and observed device deficiency.

- Report to sponsor, per the protocol requirements, all SAEs and device deficiencies that could have led to a SADE and potential/USADE or UADE.
- Report to the IRB/EC and regulatory authorities any SAEs and device deficiencies that could have led to a SADE and potential/USADE or UADE, if required by the national regulations or this protocol or by the IRB/EC, and supply BSC with any additional requested information related to the safety reporting of a particular event.
- Maintain the device accountability records and control of the device, ensuring that the investigational device is used only by authorized/designated users and in accordance with this protocol and instructions/directions for use.
- Allow the sponsor to perform monitoring and auditing activities, and be accessible to the clinical research monitor or auditor and respond to questions during monitoring visits or audit(s).
- Allow and support regulatory authorities and the IRB/EC when performing auditing activities.
- Ensure that informed consent is obtained in accordance with applicable laws, this protocol and local IRB/EC requirements.
- Provide adequate medical care to a subject during and after a subject's participation in a clinical study in the case of adverse events, as described in the Informed Consent Form (ICF).
- Inform the subject of the nature and possible cause of any adverse events experienced.
- Inform the subject of any new significant findings occurring during the clinical investigation, including the need for additional medical care that may be required.
- Provide the subject with well-defined procedures for possible emergency situations
 related to the clinical study, and make the necessary arrangements for emergency
 treatment, including decoding procedures for blinded/masked clinical investigations, as
 needed.
- Ensure that clinical medical records are clearly marked to indicate that the subject is enrolled in this clinical study.
- Ensure that, if appropriate, subjects enrolled in the clinical investigation are provided with some means of showing their participation in the clinical investigation, together with identification and compliance information for concomitant treatment measures (contact address and telephone numbers shall be provided).
- Inform, with the subject's approval or when required by national regulations, the subject's personal physician about the subject's participation in the clinical investigation.
- Make all reasonable efforts to ascertain the reason(s) for a subject's premature withdrawal from clinical investigation while fully respecting the subject's rights.

- Ensure that an adequate investigation site team and facilities exist and are maintained and documented during the clinical investigation.
- Ensure that maintenance and calibration of the equipment relevant for the assessment of the clinical investigation is appropriately performed and documented, where applicable.

16.2.1. Delegation of Responsibility

When specific tasks are delegated by an investigator, including but not limited to conducting the informed consent process, the Principal Investigator is responsible for providing appropriate training and adequate supervision of those to whom tasks are delegated. The investigator is accountable for regulatory violations resulting from failure to adequately supervise the conduct of the clinical study.

16.3. Institutional Review Board/Ethics Committee

Prior to gaining Approval-to-Enroll status, the investigational site will provide to the sponsor documentation verifying that their IRB/EC is registered or that registration has been submitted to the appropriate agency, as applicable according to national/regulatory requirements.

A copy of the written IRB/EC and/or competent authority approval of the protocol (or permission to conduct the study) and Informed Consent Form, must be received by the sponsor before recruitment of subjects into the study and shipment of investigational product/equipment. Prior approval must also be obtained for other materials related to subject recruitment or which will be provided to the subject.

Annual IRB/EC approval and renewals will be obtained throughout the duration of the study as required by local/country or IRB/EC requirements. Copies of the Investigator's reports and the IRB/EC continuance of approval must be provided to the sponsor.

16.4. Sponsor Responsibilities

All information and data sent to BSC concerning subjects or their participation in this study will be considered confidential by BSC. Only authorized BSC personnel or a BSC representative including, but not limited to Contract Research Organization (CRO) will have access to these confidential records. Authorized regulatory personnel have the right to inspect and copy all records pertinent to this study. Study data collected during this study may be used by BSC for the purposes of this study, publication, and to support future research and/or other business purposes. All data used in the analysis and reporting of this study will be without identifiable reference to specific subject name.

Boston Scientific will keep subjects' identifiable health information confidential in accordance with all applicable laws and regulations. Boston Scientific may use subjects' health information to conduct this research, as well as for additional purposes, such as overseeing and improving the performance of its device, new medical research and proposals for developing new medical products or procedures, and other business purposes.

Information received during the study will not be used to market to subjects; subject names will not be placed on any mailing lists or sold to anyone for marketing purposes.

16.4.1. Role of Boston Scientific Representatives

Boston Scientific personnel can provide technical support to the investigator and other health care personnel (collectively HCP) as needed during implant, testing required by the protocol, and follow-ups. Support may include HCP training, addressing HCP questions, or providing clarifications to HCPs concerning the operation of BSC equipment/devices (including programmers, analyzers, and other support equipment).

At the request of the investigator and while under investigator supervision, BSC personnel may operate equipment during implant or follow-up, assist with the conduct of testing specified in the protocol, and interact with the subject to accomplish requested activities. Typical tasks may include the following.

- Interrogating the device or programming device parameters to investigator-requested settings as well as operating investigational equipment
- Performing lead diagnostic testing using a Pacing System Analyzer or programmer to obtain pacing and sensing thresholds and impedance measurements
- Clarifying device behavior, operation or diagnostic output as requested by the investigator or other health care personnel
- Assisting with the collection of study data from Pacing System Analyzers, programmers, and other equipment
- Entering technical data on technical source form as long as the responsible investigator verifies and signs the completed worksheet
- Print out programming reports directly from the clinician programmer and provide original to clinical site as source documentation
- Provide technical expertise/support to subjects during office visits and/or during teleconference calls/electronic communications with the principal investigator or their delegated site staff and the subject.

In addition, BSC personnel may perform certain activities to ensure study quality. These activities may include the following.

- Observing testing or medical procedures to provide information relevant to protocol compliance
- Reviewing collected data and study documentation for completeness and accuracy

Boston Scientific personnel will not do the following.

• Practice medicine

- Provide medical diagnosis or treatment to subjects
- Discuss a subject's condition or treatment with a subject without the approval and presence of the investigator
- Independently collect critical study data (defined as primary or secondary endpoint data)
- Enter data in electronic data capture systems or on paper case report forms

16.5. Insurance

Where required by local/country regulation, proof and type of insurance coverage, by BSC for subjects in the study will be obtained.

17. Monitoring

Monitoring will be performed during the study to assess continued compliance with the protocol and applicable regulations. In addition, the clinical research monitor verifies that study records are adequately maintained, that data are reported in a satisfactory manner with respect to timeliness, adequacy, and accuracy, and that the Principal Investigator continues to have sufficient staff and facilities to conduct the study safely and effectively. The Principal Investigator/institution guarantees direct access to original source documents by BSC personnel, their designees, and appropriate regulatory authorities.

The study may also be subject to a quality assurance audit by BSC or its designees, as well as inspection by appropriate regulatory authorities. It is important that the Principal Investigator and relevant study personnel are available during on-site monitoring visits or audits and that sufficient time is devoted to the process.

18. Potential Risks and Benefits

18.1. Anticipated Adverse Events

Subjects participating in this study are subject to the same risks shared by all patients undergoing implantation of a TV-ICD system. Based on the literature and on pulse generator implant experience, Table 18.1-1 includes an alphabetical list of the possible adverse events associated with implantation of a pulse generator and/or lead system.

Currently, there is no known incremental risk of adverse events coming from the trial. If there is a difference in outcomes between the arms, the subjects will be informed of the study outcome and may choose to have their programming to the most suitable at the conclusion of the study.

Table 18.1-1: Potential Adverse Events for Implantation of a Pulse Generator and/ or Lead System Implants

Potential Adverse Events for Implantation of a P	Pulse Generator and/ or Lead System*
Air embolism	Lead dislodgment
Allergic reaction	Lead fracture
Bleeding	Lead insulation breakage or abrasion
Bradycardia	Lead perforation
Cardiac tamponade	Lead tip deformation and / or breakage
Chronic nerve damage	Local tissue reaction
Component failure	Loss of capture
Conductor coil fracture	Myocardial Infarction (MI)
Death	Myocardial necrosis
Elevated thresholds	Myocardial trauma (e.g., tissue damage, valve damage)
Erosion	Myopotential sensing
Excessive fibrotic tissue growth	Oversensing / undersensing
Extracardiac stimulation (muscle/ nerve stimulation)	Pacemaker-mediated tachycardia (PMT) (Applies to dual-chamber devices only.)
Failure to convert an induced arrhythmia	Pericardial rub, effusion
Fluid accumulation	Pneumothorax
Foreign body rejection phenomena	Pulse generator migration
Formation of hematomas or seromas	Shunting current during defibrillation with internal or external paddles
Heart block	Syncope
Heart failure following chronic RV apical pacing	Tachyarrhythmias, which include acceleration of arrhythmias and early, recurrent atrial fibrillation
Inability to defibrillate or pace	Thrombus, thromboemboli
Inappropriate therapy (e.g., shocks, and antitachycardia pacing [ATP] where applicable, pacing)	Valve damage
Incisional pain	Vasovagal response
Incomplete lead connection with pulse generator	Venous occlusion
Infection including endocarditis	Venous trauma (e.g. perforation, dissection, erosion)
Insulating myocardium during defibrillation with internal or external paddles	Worsening heart failure

From the DYNAGEN, INOGEN, ORIGEN, INCEPTA, ENERGEN, PUNCTUA, TELIGEN Physician's Technical Manual Oct 01, 2015; Part Number: 359403-002

Patients may develop psychological intolerance to a pulse generator system and may experience the following:

- Dependency
- Depression
- Fear of premature battery depletion
- Fear of shocking while conscious
- Fear that shocking capability may be lost

- Imagined shocking
- Fear of device malfunction

An addition potential risk has been identified for this study:

• Delayed therapy delivery

18.2. Anticipated Adverse Device Effects

Adverse Device Effects that are part of the listing in the previous 18.1 section are to be considered Anticipated Device Effects.

18.3. Risks Associated with Participation in the Clinical Study

Improved ICD programming to high rates and extended duration delays has been demonstrated to be safe and effective in the MADIT RIT³ clinical trial, and no incremental risks are anticipated for this study. The programming used in APPRAISE ATP aligns with the current 2015 HRS Consensus guidelines – Manufacturer Specific Translation of the HRS Consensus⁴. However, if a programming arm does not seem suitable for the individual patient, clinical judgment must be used in programming the devices after a spontaneous event has occurred.

Participation in this clinical trial occurs post device implantation, and Investigators have already chosen to implant a subject with an ICD for primary prevention indications. For women of childbearing potential, it will be at the Investigators discretion to enroll this population into the trial. No incremental risks are anticipated for this study to women of childbearing potential.

18.4. Risk Minimization Actions

Additional risks may exist. Risks can be minimized through compliance with this protocol, performing procedures in the appropriate hospital or physician office environment, adherence to subject selection criteria, close monitoring of the subject's physiologic status during research procedures and/or follow-ups and by promptly supplying BSC with all pertinent information required by this protocol.

18.5. Anticipated Benefits

There may be no benefit to the subject. However, medical science and future patients may benefit from their participation in this clinical study. If there is a superior or inferior arm, the subjects can be programmed at the conclusion of the study to the best programming suitable to their needs.

18.6. Risk to Benefit Rationale

The implantable device systems and accessories used for this clinical study will be commercially available and are considered to be standard of care for patients indicated for such implants. The risks involved with subject participation in this study are essentially the same as those for patients not participating in the study.

The recently published Expert Consensus Statement on Optimal Implantable Cardioverter Programming and Testing ¹⁵-includes information on optimal ICD programming for primary prevention patients, and the purpose is to provide evidence based expert guidance. The detection duration and rate programming in APPRAISE ATP is aligned with the recommendation for primary prevention ICD per this Consensus Statement.

19. Safety Reporting

19.1. Reportable Events by investigational site to Boston Scientific

It is the responsibility of the investigator to assess and report to BSC any event which occurs in any of following categories:

- All Serious Adverse Events
- All Device Related Adverse Events
 - PMT does not have to be reported unless the patient is symptomatic and it is true PMT. Document if there was a change in programming related to the PMT.
 - o Bradycardia only to be reported if the subject is symptomatic to the bradycardia
- All Serious Adverse Device Events
- All Device Deficiencies
- Unanticipated Adverse Device Effects/Unanticipated Serious Adverse Device Effects
- All Arrhythmic Related Events:
 - o Any treated or untreated ventricular event if not already documented as:
 - A sustained ventricular episode in the monitoring zone
 - SAF
 - A new onset of an atrial event not reported in the Medical History
 - ATR episodes do not need to be reported if it is a response to a known and/or previously reported atrial arrhythmia
- Syncope

- o Including reports of near syncope, which could include but not limited to symptoms of dizziness, lightheadedness, fainting
- For subjects with a HeartLogic Alert, any change in heart failure therapy which requires IV treatment should be reported as an AE.
- New findings/updates in relation to already reported events

For Event reporting the medical diagnosis must be reported. In case the diagnosis is not available, individual symptoms can be reported to fulfill reporting timelines. If a diagnosis becomes available at a later stage, it must be added to the reported event.

If it is unclear whether or not an event fits one of the above categories, or if the event cannot be isolated from the device or procedure, it must be submitted as an adverse event and/or device deficiency.

Any AE event required by the protocol, experienced by the study subject after informed consent and once considered enrolled in the study (as defined in study subject classification section), whether during or subsequent to the procedure, must be recorded in the eCRF.

Underlying diseases are not reportable as AEs unless there is an increase in severity of frequency during the course of the investigation. For centers in Austria cancer must always be reported as a Serious Adverse Event. Death events itself are not be recorded as an SAE, but must be reflected as an outcome of ONE (1) specific SAE/ SADE or USADE (see Table 20.2-1 for Event definitions).

Refer to Section 18 for the known risks associated with the study device(s).

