11.7. Subjects who are monitored on LATITUDE

For subjects who are remotely monitored, the wireless LATITUDE[™] Patient Management system will be utilized to collect and store treated tachyarrhythmia episodes. Alerts, diagnostic data, and all treated ventricular episodes EGMs are collected for endpoint evaluation directly from the LATITUDE database. Applicable reports will be uploaded remotely into the study database from the LATITUDE BSC team as defined on the data collection schedule on Table 11.1-2.

After programming to treatment arm (Index procedure Day 0), subjects who are remotely monitored with the LATITUDE system must have the following yellow alerts programmed on in the LATITUDE database:

- Ventricular shock therapy delivered to convert arrhythmia
- Accelerated ventricular arrhythmia episode
- Atrial Arrhythmia burden of at least {>1, 3, 6, 12, 18, or 24} hours in a 24 hour period
- Patient triggered event stored

If the HeartLogic feature is available in the implanted device, all subjects with this feature will be monitored by the LATITUDE BSC team for the specific HeartLogic alerts. In the event of an alert, a report will be uploaded by the LATITUDE BSC team into the study database.

Table 11.7-1: LATITUDE Follow Up Data – Device Report Upload

Data Collection Requirement	Retention of Original Source Documentation
LATITUDE Nominal Device ReportVentricular arrhythmia episodesLATITUDE Alerts	Reports uploaded into the study database by BSC LATITUDE team

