12.1.6.2. Latitude Alerts

The purpose of this tertiary objective is to (1) characterize the usage rates of HeartLogic among study patients, (2) characterize the alert rates among patients using HeartLogic, and (3) evaluate if usage and/or alerts are associated with changes in clinical therapy, the occurrence of adverse events, or other patient outcomes.

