19.2. Definitions and Classification

Adverse event definitions are provided in Table 19.2-1. Administrative edits were made on the definition of serious adverse event from ISO 14155and MEDDEV 2.7/3 for clarification purposes. Adverse events to be reported per section 19.1.

Table 19.2-1: Safety Definitions

Term	Definition
Adverse Event (AE)	Any untoward medical occurrence, unintended disease or injury, or any untoward clinical signs (including an abnormal laboratory finding) in
Ref: ISO 14155	subjects, users or other persons, whether or not related to the investigational medical device.
Ref: MEDDEV 2.7/3	NOTE 1: This includes events related to the investigational medical device or comparator.
	NOTE 2: This definition includes events related to the procedures involved.

Table 19.2-1: Safety Definitions

Term	Definition
2 3 3 3 3	NOTE 3: For users or other persons, this definition is restricted to events related to the investigational medical device.
Adverse Device Effect (ADE)	Adverse event related to the use of an investigational medical device
Ref: ISO 14155 Ref: MEDDEV 2.7/3	NOTE 1: This includes any adverse event resulting from insufficiencies or inadequacies in the instructions for use, the deployment, the implantation, the installation, the operation, or any malfunction of the investigational medical device.
	NOTE 2: This definition includes any event resulting from use error or intentional abnormal use of the investigational medical device.
Serious Adverse Event (SAE)	Note: This definition meets the reporting objectives and requirements of ISO 14155 and MEDDEV 2.7/3.
Ref: ISO 14155	Adverse event that:
D.C. MEDDEU 2 7/2	Led to death,
Ref: MEDDEV 2.7/3	• Led to serious deterioration in the health of the subject as defined by either:
	o a life-threatening illness or injury, or
	o a permanent impairment of a body structure or a body function, or
	 in-patient hospitalization or prolongation of existing hospitalization , or
	o in medical or surgical intervention to prevent life-threatening illness
	 injury or permanent impairment to a body structure or a body function
	Led to fetal distress, fetal death, or a congenital abnormality or birth defect.
	NOTE 1: Planned hospitalization for a pre-existing condition, or a procedure required by the clinical investigational plan, without a serious deterioration in health, is not considered a serious adverse event.

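### Non-serious IV heart-failure treatment is a named reportable AE only after a HeartLogic alert, which biases the planned alert-to-AE comparison upward

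*Combined protocol and SAP*

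**What the plan says.** AE collection in this trial is selective. Section 19.2 refers back to a list ("Adverse events to be reported per section 19.1"), and that list is in 19.1. Most of its lines apply to every subject, including "All Serious Adverse Events" and "All Device Related Adverse Events". One does not: "For subjects with a HeartLogic Alert, any change in heart failure therapy which requires IV treatment should be reported as an AE". No matching line covers subjects who never had an alert or whose device lacks the feature. The line also sets no time window, so it is unclear whether IV treatment given before a subject's first alert counts.

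Section 11.7 describes who can generate an alert: "If the HeartLogic feature is available in the implanted device, all subjects with this feature will be monitored by the LATITUDE BSC team".

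Section 12.1.6.2 sets a tertiary objective in three parts: usage rates, alert rates, and to "evaluate if usage and/or alerts are associated with changes in clinical therapy, the occurrence of adverse events, or other patient outcomes". The third part does not restrict the adverse events to those collected on the same terms in the groups being compared.

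**The concern.** When an outcome is recorded under a wider definition in exposed subjects than in unexposed subjects, the two will differ even if the exposure carries no information. Here the exposure is the alert and the outcome is the AE. A site that follows 19.1 exactly would file an AE for non-serious IV heart-failure treatment in a subject who had an alert, and would have no named reason to file one for the same treatment in a subject who had not. The usage comparison is affected as well, because a subject without HeartLogic can never meet the condition.

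At stake is how a positive finding in part (3) would be read. An excess of AEs after alerts could be presented as evidence that alerts identify deteriorating patients when part or all of it comes from the reporting rule. Covariate adjustment cannot restore events that were never recorded.

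**Working it through.** The plan gives no event rate, sample size or test for this objective, so there is no figure to reproduce. The check has two steps.

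**Step 1: which IV heart-failure episodes are recorded as AEs?**

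| Episode | Subject with an alert | Subject without an alert |
|---|---|---|
| Involves admission, so serious under 19.2 ("in-patient hospitalization or prolongation of existing hospitalization") | Reportable | Reportable |
| Serious by another 19.2 route | Reportable | Reportable |
| Device related | Reportable | Reportable |
| Neither serious nor device related | Reportable under the HeartLogic line | No named category |

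The asymmetry is confined to the last row. Two other sentences in 19.1 could bring in some of those episodes without an alert. One is the catch-all ("If it is unclear whether or not an event fits one of the above categories"). The other lifts the exemption for underlying disease when it worsens. Neither states a rule equal to the HeartLogic line.

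**Step 2: how large could the distortion be?** The inputs below are assumptions, because the documents give none of them.

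- The true rate of IV heart-failure episodes is the same with and without an alert (no association).
- With an alert, all episodes are reported.
- Without an alert, a share s is reported, by any of the routes above.
- b is the number of other reportable AEs per true IV episode, equal in both groups.

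Apparent rate ratio for IV heart-failure AEs = 1/s:

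- s = 1: 1.00
- s = 0.9: 1/0.9 = 1.11
- s = 0.75: 1/0.75 = 1.33
- s = 0.5: 1/0.5 = 2.0

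Apparent rate ratio for all reportable AEs = (b + 1)/(b + s). At s = 0.5:

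- b = 1: 2/1.5 = 1.33
- b = 3: 4/3.5 = 1.14
- b = 10: 11/10.5 = 1.05

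For users against non-users, if a share a of users has an alert, the ratio for IV heart-failure AEs is (a + (1 − a)s)/s. With a = 0.5 and s = 0.5 this is 0.75/0.5 = 1.5, which lies between 1 and 1/s.

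Every ratio exceeds 1 whenever s is below 1, and equals 1 when the rule is the same for both groups.

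**The case against.** The strongest reply is that other provisions close much of the gap. Admission is only one route to an SAE. Under 19.2, life-threatening illness also qualifies, as does medical intervention to prevent it or to prevent permanent impairment, so some outpatient IV treatment is an SAE in anyone. Table 18.1-1 lists worsening heart failure among the potential adverse events, and Table 19.3-1 classes events whose relatedness cannot be assessed as possibly related. Some episodes will therefore be reported as device related whatever the alert status. The catch-all and the underlying-disease sentence may bring in more. All of this stands and it raises s, but it does not make the rule equal. If those sentences already made every such episode reportable, the HeartLogic line would be largely redundant. At best the text is ambiguous and sites may apply it differently.

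The reply also limits how far the point reaches. A reader might infer that any IV heart-failure treatment is reported only after an alert; the SAE and device-related lines contradict that. A reader might also infer a built-in association with therapy changes. The data collection schedules in 11.1 and the phone visits in 11.7.1 collect cardiac medication changes regardless of alert, so the bias reaches therapy changes only if IV-therapy AEs are used to measure them, and 12.1.6.2 names no source. Nor is the whole tertiary objective unanswerable. Usage rates and alert rates are untouched, and part (3) can be addressed with SAEs, deaths and medication changes.

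Finally, 12.1.6.2 fixes no particular AE comparison, so the bias arises only if the analysis counts AEs collected under the HeartLogic line. That is true, and it is why one sentence in the plan can prevent it.

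**Conclusion.** The point holds for one class of event: IV heart-failure treatment that is neither serious nor device related. For that class, AE ascertainment depends on alert status, and both the alert-to-AE and usage-to-AE associations in part (3) of 12.1.6.2 are biased upward. The direction follows from the text. The size does not, since s, b and the share of users with an alert are all assumed. The 1/s figures describe IV heart-failure AEs alone; an analysis of all reportable AEs would show less.

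The consequence is limited to one part of a tertiary objective with no stated hypothesis or power. None of the primary or secondary endpoints uses these AEs. It is still worth correcting, because the remedy is small and the missing reports cannot be recovered later.

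**What to change.** In 12.1.6.2, add that the association of HeartLogic usage or alerts with adverse events will use only event types reportable identically with and without an alert. For data collected under the current rule, exclude AEs reported solely under the HeartLogic line. The simplest way is to restrict the comparison to SAEs, since seriousness is assessed on the AE form (Table 19.4-1). State also which data source measures therapy changes, and what time window around an alert applies. This needs no new data collection and can be made in an amended SAP before the blind is broken, as 12.3.4 allows.

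Preferably, also change the 19.1 line so that it applies to all subjects. A narrower choice is all subjects with a HeartLogic-capable device, which is enough for the alert comparison but not for users against non-users. The cost is some additional non-serious AE forms and, because the change bears on the scientific integrity of the data, a protocol amendment with approvals under section 14. It requires no extra visit or procedure.
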